15.2.2.5 CDAI

The CDAI is a composite index (without acute-phase reactant) for assessing disease activity. CDAI is based on the simple summation of the swollen and tender joint counts based on 28 joints along with the Patient's and Physician's Global Assessment of Disease Activity (VAS) for estimating disease activity. The CDAI ranges from 0 to 76.

The CDAI is calculated based on the following formula:

$$CDAI = SJC28 + TJC28 + GH + PGA$$

where:

- TJC28 = 28 joint count for tenderness
- SJC28 = 28 joint count for swelling
- GH = the general health component of the DAS (i.e., Patient's Global Assessment of Disease Activity assessed using a scale of 1 to 100 where 100 is maximal activity; For analyses, GH will be divided by ten and converted to a 0.5 scale, i.e. 0, 0.5, 1, 1.5 etc. where [0-0.25] = 0, [0.25-0-75] = 0.5, [0.76-1.25] = 1, etc.)
- PGA = Physician's Global Assessment of Disease Activity assessed using a scale of 1 to 100 where 100 is maximal activity. For analyses, PGA will be divided by ten and converted to a 0.5 scale, i.e. 0, 0.5, 1, 1.5 etc. where [0-0.25] = 0, [0.25-0-75] = 0.5, [0.76-1.25] = 1, etc.

Summary statistics will be presented for the actual CDAI values and change from baseline, by visit and treatment arm, at Weeks 2, 4, 8, 12, 24 and 52.

Line graphs will also be provided to display the change from baseline over time for CDAI, by treatment arm.

15.2.2.6 SDAI

The SDAI is the numerical sum of five outcome parameters: tender and swollen joint counts (based on a 28-joint assessment), Patient's and Physician's Global Assessment of Disease Activity (VAS) and level of CRP (mg/dL).

The SDAI is calculated based on the following formula:

$$SDAI = SJC28 + TJC28 + GH + PGA + CRP$$

where:

- TJC28 = 28 joint count for tenderness
- SJC28 = 28 joint count for swelling
- GH = the general health component of the DAS (i.e., Patient's Global Assessment of Disease Activity assessed using a scale of 1 to 100 where 100 is maximal activity; For analyses, GH will be divided by ten and converted to a 0.5 scale, i.e. 0, 0.5, 1, 1.5 etc. where [0-0.25] = 0, [0.25-0-75] = 0.5, [0.76-1.25] = 1, etc.)
- PGA = Physician's Global Assessment of Disease Activity assessed using a scale of 1 to 100 where 100 is maximal activity. For analyses, PGA will be divided by ten and converted to a 0.5 scale, i.e. 0, 0.5, 1, 1.5 etc. where [0-0.25] = 0, [0.25-0-75] = 0.5, [0.76-1.25] = 1, etc.
- CRP = C-reactive protein in mg/dL.

Summary statistics will be presented for the actual SDAI values and change from baseline, by visit and treatment arm, at Weeks 2, 4, 8, 12, 24, and 52.

Line graphs will also be provided to display the change from baseline over time for SDAI, by treatment arm.

15.2.2.7 ACR/EULAR Boolean Remission

Following the Boolean-based definition of remission of ACR/EULAR, at any timepoint, a subject must satisfy all of the following: tender joint count ≤ 1 , swollen joint count ≤ 1 , CRP ≤ 1 mg/dL, and Patient's Global Assessment Of Disease Activity ≤ 1 (0-10 VAS).

The proportion of subjects with ACR/EULAR remission at Weeks 2, 4, 8, 12, 24, and 52 will be reported along with 95% CIs.

15.3 Other Secondary Endpoint Analyses

15.3.1 Quality of life

The three QoL questionnaires completed are the Health Assessment Questionnaire-Disability Index (HAQ-DI), the European Quality of Life – 5 Dimensions and 5 Levels (EQ-5D-5L) and the 36-item Short-Form Health Survey (SF-36).

A summary of QoL questionnaire completion, including reason for non-completion will be presented by visit and treatment arm.

Summary statistics for absolute value and absolute change from baseline will be presented for domains and/or total scores at baseline and at Weeks 12, 24, and 52 by treatment arm.

The summaries will be presented using both the ITT and the PP analysis sets.

15.3.1.1 European Quality of Life - 5 Dimensions and 5 Levels (EQ-5D-5L)

The EQ-5D-5L consists of two components - the EQ-5D descriptive system and the EQ visual analogue scale (EQ VAS). The descriptive system comprises the following five dimensions:

- Mobility
- Self-care
- Uusual activities
- Pain/discomfort
- Anxiety/depression.

Each dimension has five levels coded from 1 to 5 as follows:

- No problems (1)
- Slight problems (2)
- Moderate problems (3)
- Severe problems (4)
- Unable to function (mobility, self-care, and usual activities) or extreme problems (pain/discomfort and anxiety/depression) (5).

Subject response to this component results in a 1-digit number expressing the level selected for each dimension. The digits for five dimensions can be combined into a 5-digit number.

The 5-digit health state represents the scores for mobility, self-care, usual activities, pain/discomfort and anxiety/depression, strictly in that order of the dimensions.

Given that there are five domains and five scores per domain, there are 3125 potential health states.

For example, if a subject had no problems for any dimension, their 5-digit health state would be 11111, while a subject with no problems for mobility, slight problems for self-care, severe

problems with usual activities, extreme pain and moderate anxiety/depression would have a 5-digit state of 12453.

Each of these 3125 potential health states will be converted into a single summary index value using the EQ-5D-5L Crosswalk Index Value Calculator, downloaded from the EuroQol website.

An index value of 1 represents perfect health, the 5-digit health state would be 11111; the lowest, and therefore worst, value is -0.109, where the 5-digit health state would be 55555.

Respondents indicate their self-rated health on the EQ VAS, a 20 cm vertical, visual analogue scale numbered from 0 to 100 where the endpoints are labelled 'Best health you can imagine' (100) and 'Worst health you can imagine' (0). This information can be used as a quantitative measure of health outcome as judged by the individual respondents.

Summaries of the absolute values and absolute change from baseline for the index value and VAS score will be presented as described in Section 15.3.1.

15.3.1.2 Health Assessment Questionnaire – Disability Index (HAQ-DI)

This questionnaire consists of 20 questions, referring to the following eight domains:

- Dressing/grooming
- Getting up
- Eating
- Walking
- Personal care
- Reach
- Grip
- Common daily activities.

Each domain has at least two component questions. There are four possible responses for each component.

- 0 =without any difficulty
- 1 = with some difficulty
- 2 =with much difficulty
- 3 = unable to do.

A domain score is determined from the highest score of the components in that domain (except when aids and devices are taken into account). For example, if there are three components in a domain and the responses were 1, 2 and 0 to the components in the domain, then the score for the domain would be 2.

[figure not shown]
To calculate the HAQ-DI, the subject must have a domain score for at least six of the eight domains. The HAQ-DI score, or functional disability index (FDI), is the sum of the domain scores, divided by the number of domains that have a score (denominator is in the range 6 to 8).

The explanations below describe how the HAQ-DI score is calculated when we have missing answers to questions or when more than one answer is given for a question.

[figure not shown]
- If any domain consists of two questions and has one missing response, then the non-missing response will be used as the value for the domain. If a domain consists of three questions and has one missing response then the domain score will be the higher of the two responses. If a domain consists of three questions and has two missing responses then the domain will be considered missing.
- When there are no aids or devices used, the domain score is not modified. If the domain responses are missing and no aids or devices are listed then the domain will be considered missing.
- If aid or device and/or help for another person are checked for a domain:
 - o If the domain score is missing, then the score for that domain will reflect the use of the aid or device, ie it will be scored as 2.
 - o If the domain score is not missing, the score for that domain is raised from 0 or 1 to 2 and unchanged if already scored at 2 or 3
- The HAQ-DI will be set to missing if more than two of the domain scores are missing. In the event that one or two domain scores are missing, the final HAQ-DI score will be derived by dividing the total of the remaining domain scores by the number of non-missing domains.
- If a subject marks two responses adjacent to each other for an item on the HAQ-DI, the 'worst case' (ie response with the greater difficulty) will be used in the analysis. However, if a subject marks two responses which are not adjacent to each other, or marks more than two responses, the item will be coded as missing in the analysis.

Summaries of the absolute values and absolute change from baseline for HAQ-DI score (FDI) will be presented as described in Section 15.3.1.

15.3.1.4 Injection Site pain

The subject's reported perception of injection site pain will be measured on a VAS immediately after, 15 minutes after, and 1 hour after the 3rd, 4th and 5th injection administrations. The VAS ranges from 0 (no pain) to 100 (worst possible pain).

Summaries of the absolute values and absolute change from Week 4 (3rd dose) for the pain scores will be presented by timepoint (immediately after, 15 minutes after, and 1 hour after) and treatment arm for the SAF analysis set.

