#### Injection-site pain

- Mean change in injection site pain on a visual analog scale (VAS), evaluated during 3 administrations of IMP (doses 3 to 5) (immediately post-injection, 15 minutes post-injection, and 1 hour post-injection)

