### 4.2.2 Other Secondary Objectives

Other secondary objectives are as follows:

- To evaluate the immunogenicity profile of MSB11022-CCI compared to Humira® in patients with moderately to severely active RA up to Week 52
- To further compare the efficacy and safety of MSB11022-CCI compared to Humira® in patients with moderately to severely active RA up to Week 52
- To compare quality of life (QoL) and physical function on MSB11022-CCI with Humira® in patients with moderately to severely active RA
- To compare injection site pain levels of MSB11022-CCI versus Humira®.

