## Injection Site Pain

The patient's reported perception of pain will be measured on a VAS where the slash drawn by the patient represents pain of increasing intensity. The first 2 injections will be administered by qualified personnel. The next three doses of IMP (3-5) will be self-administered by the patient and injection site pain will be assessed. Pain will be recorded immediately after, 15 minutes after, and 1 hour after the injections received by the patient.

Results will be expressed in millimeters measured between the left end of the scale and the crossing point of the vertical line of the tick. This procedure is applicable for all VAS scales used in the trial.

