#### Other Secondary Endpoints

- Safety
  - Occurrences of TEAEs and SAEs including and up to the 4-month Safety Evaluation visit (AEs will be recorded at each visit: screening, baseline [Week 0], and Weeks 2, 4, 8, 12, 24, 36, 48, and 52, and 4-week and 4-month Safety Follow-up)
  - Vital signs at screening, baseline and at Weeks, 2, 4, 8, 12, 24, 36, 48, and 52
  - Physical examination at screening, baseline and at Weeks 2, 4, 8, 12, 24, 36, 48, and 52
  - Hematology, urinalysis and biochemistry analysis at screening, baseline and at Weeks 2, 4, 12, 24, 36, 48, and 52
  - ANA and anti-dsDNA at baseline and at Weeks 24 and 52
  - 12-lead ECG at screening, Weeks 12, 24, and 52

- Immunogenicity
  - ADA to adalimumab and ADA titer including and up to Week 52
  - Neutralizing ADA to adalimumab including and up to Week 52
- Efficacy
  - ACR20 at Weeks 2, 4, 8, 24, and 52
  - ACR50 response rates at Weeks 2, 4, 8, 12, 24, and 52
  - ACR70 response rates at Weeks 2, 4, 8, 12, 24, and 52
  - Change from baseline in DAS28-ESR to Weeks 2, 4, 8, 12, 24, and 52
  - Proportion of patients with DAS28 low disease activity and remission at Weeks 2, 4, 8, 12, 24, and 52
  - Change from baseline in SDAI at Weeks 2, 4, 8, 12, 24, and 52
  - Change from baseline in CDAI at Weeks 2, 4, 8, 12, 24, and 52
  - ACR/EULAR Boolean remission rates at baseline, Weeks 2, 4, 8, 12, 24, and 52
- Quality of Life (QoL) and Physical Function
  - At baseline, then at Weeks 12, 24, and 52:
    - HAQ-DI - Health Assessment Questionnaire – Disability Index
    - SF-36 - 36-item Short-Form Health Survey
    - EQ-5D-5L - The EuroQoL-5D-5L dimension instrument
  - Injection site pain
    - Mean change in injection site pain on a VAS, evaluated during 3 (doses 3-5) administrations of IMP

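### The injection-site pain endpoint is a change from the 3rd dose of the same product, which does not match the objective of comparing pain levels; name absolute VAS as the endpoint and add a between-arm difference with 95% CI

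*SAP*

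**What the plan says.** **Objective.** Protocol 4.2.2 lists, among the other secondary objectives, "To compare injection site pain levels of" the test product versus Humira.

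**Endpoint.** The protocol synopsis names "Mean change in injection site pain on a visual analog scale (VAS), evaluated during 3 administrations of IMP", scored at three times: "immediately post-injection, 15 minutes post-injection, and 1 hour post-injection". Protocol 8.3.2 has "Mean change in injection site pain on a VAS, evaluated during 3 (doses 3-5) administrations of IMP". SAP section 6 repeats the synopsis endpoint. None of these places says what the change is measured from.

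**Reference point.** Only SAP 15.3.1.4 supplies one. It plans "Summaries of the absolute values and absolute change from Week 4 (3rd dose) for the pain scores", laid out by post-injection time ("immediately after, 15 minutes after, and 1 hour after) and treatment arm for the SAF analysis set"). On the scale it states: "The VAS ranges from 0 (no pain) to 100 (worst possible pain".

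**When pain is scored.** Protocol 7.7.2 has staff give the first two injections and then says: "The next three doses of IMP (3-5) will be self-administered by the patient and injection site pain will be assessed". The Schedule of Assessments places these scores at Weeks 4, 6 and 8. There is no score before treatment or at doses 1 and 2.

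**Reporting rules.** Protocol 8.5.1 and SAP 11 and 11.1 give continuous variables a mean, SD, 95% CI, median and range per arm. No between-arm difference is specified for pain.

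**The concern.** The objective concerns how much each product hurts. The named endpoint concerns how much pain moves after the 3rd injection. By then every patient has been on the randomised product since baseline, so the reference score already carries any product effect, and subtracting it removes whatever part of that effect is stable across doses.

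A persistent difference between two formulations is a natural form for an injection-pain effect, and it is the form the change score cannot show. A report built around the named endpoint would lead with two mean changes. If both were near zero, they could be misread as similar pain. The absolute tables give three doses by three times, nine cells per arm, with no between-arm summary named in advance. The choice of which cells to stress could then be made after unblinding.

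**Working it through.** The documents give no SD, expected difference, margin or power for pain, so there is no planned figure to reproduce. The check has two parts.

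**1. What each measure estimates**

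Let the mean VAS at dose j (j = 3, 4, 5) and a given post-injection time be μ_j on Humira and μ_j + D_j on the test product.

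- Absolute contrast at dose j: (μ_j + D_j) − μ_j = D_j.
- Contrast in change from dose 3: [(μ_j + D_j) − (μ_3 + D_3)] − [μ_j − μ_3] = D_j − D_3.

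If the difference is constant (D_3 = D_4 = D_5 = D), the absolute contrast is D and the change contrast is 0, whatever the size of D. If the difference grows or shrinks between doses, the change contrast shows only that drift.

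A simulation with 200,000 patients per arm (assumed SD 20 mm, correlation 0.5) agrees:

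| True constant D (mm) | Absolute contrast, doses 3–5 (mm) | Change contrast, doses 4 and 5 (mm) |
|---|---|---|
| 5 | 4.89 to 4.93 | 0.00 and 0.04 |
| 10 | 9.99 to 10.06 | 0.06 and 0.07 |
| 20 | 19.92 to 20.10 | 0.14 and 0.18 |

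The small non-zero changes are simulation noise.

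Reading change as the fall within one injection, from immediately after to 1 hour after, would not help. That measures how quickly pain resolves, not its level.

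**2. Precision of a between-arm difference in absolute VAS**

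Inputs: n = 130 per arm (Protocol 8.1). Assumptions: SD 15 to 25 mm, within-patient correlation ρ = 0.5 between doses, complete scores at all three doses.

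- One dose: half-width = 1.96 × SD × √(2/130). For SD 20: 1.96 × 20 × 0.1240 = 4.9 mm.
- Mean of three doses: the variance is multiplied by (1 + 2ρ)/3 = (1 + 1)/3 = 2/3, so the half-width is multiplied by √(2/3) = 0.816. For SD 20: 4.86 × 0.816 = 4.0 mm.

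| Assumed SD (mm) | One dose (mm) | Three-dose average (mm) |
|---|---|---|
| 15 | 3.6 | 3.0 |
| 20 | 4.9 | 4.0 |
| 25 | 6.1 | 5.0 |

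**The case against.** Several points count against reading this more strongly.

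- **Levels are reported.** A reader might infer that the objective goes unanswered. The documents do not support that. SAP 15.3.1.4 plans absolute values in the same sentence as the change, by time and arm, and the general rules attach a mean, SD and 95% CI for each arm. A constant difference would be visible in those tables.
- **Cancellation is conditional.** A reader might also infer that the plan would make the products look equally painful whatever the truth. That is wrong twice over: the absolute summaries would show the difference, and the change score loses only what is constant across doses 3 to 5.
- **Pain is also captured elsewhere.** Protocol 7.4.2.1 has injection-site pain at injections 3 to 5 reported as an adverse event. SAP 16.1.1 summarises injection-site reactions by arm, with incidence rates and exact 95% CIs. This compares reported events, not VAS levels, so it supplements the pain score without replacing it.
- **The study is descriptive.** DAS28-ESR, CDAI, SDAI and the quality-of-life scores also have no stated between-arm difference. This shows that the omission is not peculiar to pain. It does not rule out an estimate: the SAP gives a between-arm 95% CI for ACR20 (15.2.1) and a half-width for the difference in the most common hypersensitivity events (15.1).
- **The precision figures do not measure the defect.** They describe the proposed replacement and rest on assumed values. The Week 6 score is recorded at home, so completeness may fall short of 130 per arm.

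What stands after this is the mismatch between named endpoint and objective, and the absence of a specified between-arm pain estimate.

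**Conclusion.** The point holds as a mismatch between endpoint and objective, not as a missing analysis of pain levels. With the SAP's 3rd-dose reference, the named endpoint has an expected between-arm contrast of exactly 0 for any product difference that is constant over doses 3 to 5. That result is algebraic and needs only the constancy assumption. The planned absolute summaries show levels descriptively, but they are not the endpoint the protocol names.

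The data already planned would support a direct estimate. The 95% half-widths of about 3.6 to 6.1 mm (one dose) and 3.0 to 5.0 mm (three-dose average) depend on the assumed SD, correlation and completeness. The matter concerns one of the other secondary objectives and does not touch the primary endpoint. It is worth correcting because the correction is small.

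**What to change.** 1. In Protocol 8.3.2, the synopsis and SAP section 6, name the endpoint as the absolute VAS score immediately, 15 minutes and 1 hour after doses 3 to 5.
2. In SAP 15.3.1.4, specify the between-arm mean difference with 95% CI at each post-injection time, averaged over the three doses per patient or taken from a repeated-measures model. State how patients with fewer than three scores are handled.
3. Keep change from dose 3 as a description of trend only, and say that it does not compare pain levels between products.
4. Reconcile the analysis set: SAP Table 1 (section 10.2) ticks both ITT and SAF for injection site pain, while 15.3.1.4 names SAF only.

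Cost: endpoint and SAP wording plus one table, fixed before unblinding. No new data are needed.

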15.3.2 Immunogenicity Analysis

Immunogenicity data will be summarized by treatment arm for the SAF analysis set. Overall ADA status (negative or positive, where positive is defined as at least one positive result post-dose) will be summarized as well as ADA titers and presence or absence of neutralizing antibodies.

Time to positive ADA status, calculated from Trial Day 1, will also be analyzed. Subjects who discontinued the study or were lost to follow-up, or had not reached the endpoint of interest at the time of analysis, will be censored at the date of last sample collection. Results will be summarized by means of Kaplan-Meier curves together with a summary of associated statistics (median, 95% confidence interval) and the number of subjects under risk.

Summary statistics will be presented for the actual titer values, by treatment arm and visit up to Week 52. Boxplots will be produced to present the ADA titer results graphically. The boxplots will present Q1, Q3, median, minimum and maximum.

The number and percentage of ADA positive and NAb positive subjects will be presented for each visit up to Week 52.

The analysis exploring the correlation between ADA and efficacy, PK and safety will be described in Sections 15.3.2.1, 15.3.3.1, and 16.6 respectively.

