## 7.2.4 **Immunogenicity**

A blood sample will be collected at screening for assay validation purposes only, no results will be reported and at baseline (on Day 1/Week 0 before IMP administration).

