12.4 Other Baseline Characteristics

History of rheumatoid arthritis (time (in months) since diagnosis relative to informed consent) will be summarized by treatment arm and overall for the ITT and PP analysis sets. Baseline assessments for the ACR component variables (tender joint count (TJC), swollen joint count (SJC), Patient's and Physician's Global Assessment of Disease Activity, Patient's Assessment of Arthritis Pain, Patient's Assessment of Physical Function as measured by the HAQ-DI and CRP), DAS28-ESR, CDAI, SDAI and tuberculosis assessment at baseline will also be summarized by treatment arm and overall for the ITT and PP analysis sets.

Methotrexate dose at baseline will be summarized by treatment arm and overall for the ITT and PP analysis sets.

Height (cm), weight (kg), BMI (kg/m²), vital signs (body temperature, heart rate, respiration rate and blood pressure), and ECG interpretation at baseline will be summarized by treatment arm for the ITT and PP analysis sets.

Height will be presented in centimeters (cm) and weight will be presented in kilograms (kg). The conversion factors used will be:

- Height in cm = Height in inches $\times 2.54$
- Weight in kg = Weight in pounds / 2.2046

ADA status, ADA titer and NAbs status at baseline will be summarized by treatment arm for the ITT and the PP analysis sets.

13 Previous or Concomitant Medications/Procedures

Medications which are taken by subjects other than study medications (MSB11022 or Humira) will be defined as previous or concomitant medication.

Previous medications will be defined as those that started and stopped before the first dose of study medication.

Concomitant medications will be defined as those that started before or during the treatment period (and up to the 4 week Safety Follow-up visit or 28 days after the last dose of study drug, whichever comes later) and finished during the treatment period or are ongoing.

In case the date values will not allow to unequivocally allocate a medication as previous or concomitant, the medication will be considered as a concomitant medication.

Previous and concomitant medications will be summarized by Anatomical Therapeutic Chemical (ATC) Level 2 and PT. Medications will be coded by the Enhanced World Health Organization Drug (WHODrug) dictionary, version September 2016 or later. In case multiple ATC's are assigned to a drug, all ATC-2nd level will be used for reporting.

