15.3.2.1 Efficacy/ADA Correlation Analysis

Summary tables will present ACR20 and ACR50 by ADA status. A line graph will also be provided to display the ACR20 response rate over time by treatment arm and ADA status.

Boxplots displaying *DAS28-ESR* change from baseline at Week 12 by both ADA status and lower and upper quartiles of ADA titers will be produced. The change from baseline for *DAS28-ESR* will be the value for the specified visit, the ADA status or ADA titers will be the values for the treatment period.

The ADA titer quartiles will be defined using the highest ADA titer value from each subject for the period from baseline to Week 12 where subjects with ADA negative for the whole period will be assigned to a titer value of 0. ADA titers will be computed by splitting the subjects by treatment arm, taking their highest ADA titer values for the treatment period, arranging the values from smallest to largest and splitting into quartiles.

Line graphs will also be provided to display the change from baseline over time for continuous efficacy endpoints (TJC28, SJC28, ESR, DAS28-ESR, CDAI, SDAI), split by treatment arm and ADA status at a specified visit.

In addition, scatterplots of percentage change from baseline in continuous efficacy endpoints (DAS28-ESR, CDAI, SDAI) vs titer on log2 scale (if appropriate) will be generated for each treatment with separate symbols (if appropriate) for each study week.

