Figures of mean concentration-time data for trough adalimumab serum concentrations will be presented on linear (\pm SD) and semi logarithmic scales by treatment arm, and with treatments overlaid together as appropriate. Individual and mean trough adalimumab concentration-time data by treatment arm and visit week will be graphically presented on linear scale.

Concentrations for adalimumab will be listed and summarized by treatment arm and by ADA status (positive/negative) to assess the correlation between PK and ADA data. Also, a figure of mean (\pm SD) concentration-time data for adalimumab samples by ADA status (positive/negative) on linear scale will be presented by treatment arm, as appropriate.

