16.6 Safety/ADA Correlation Analysis

The following frequency tables by treatment arm, status of ADA (negative or positive, where positive is defined as at least one positive result post-dose), primary SOC and PT will be provided for:

[figure not shown]
- TEAEs
- AESIs (Hypersensitivity)
- Injection Site Reactions

The tables will be repeated for neutralizing antibody positive versus negative status.

[figure not shown]
17 Reporting Conventions and Data Handling

[figure not shown]
The reporting conventions will follow those detailed in the Biostatistical Output Assembly (BOA) v2.0 document.

19 References

- FDA, Guidance for Industry RA: Developing Drug Products for Treatment, 2013.
- Ware JE Jr and Sherbourne CD. The MOS 36-item short-form health survey (SF-36). I. Conceptual framework and item selections. Med Care. 1992; 30(6):473-483.

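### ADA-positive means any post-dose positive whatever the baseline result, so pre-existing reactivity enters ADA incidence, time to ADA and the ADA-status tables; the size depends on a baseline rate the documents do not give

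*SAP*

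**What the plan says.** **Definition.** In SAP 15.3.2, overall ADA status is positive when there is "positive is defined as at least one positive result post-dose". SAP 16.6 splits TEAEs, hypersensitivity events and injection site reactions by "status of ADA (negative or positive, where positive is defined as at least one positive result post-dose", and repeats the tables by neutralizing antibody status.

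**Time to ADA.** SAP 15.3.2 adds: "Time to positive ADA status, calculated from Trial Day 1, will also be analyzed". It has a censoring rule but no rule for subjects already positive on Day 1.

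**Correlation displays.** SAP 15.3.2.1: "Summary tables will present ACR20 and ACR50 by ADA status". Its titer quartiles use the "highest ADA titer value from each subject for the period from baseline to Week 12", although the same paragraph also refers to the treatment period. SAP 15.3.3.1: "Concentrations for adalimumab will be listed and summarized by treatment arm and by ADA status (positive/negative". None of these sets a baseline condition. Some line graphs in 15.3.2.1 use status at a given visit instead of overall status, again without reference to baseline.

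**Baseline data.** Protocol 7.2.4 has a sample taken "at baseline (on Day 1/Week 0 before IMP administration"). SAP 12.4 says "ADA status, ADA titer and NAbs status at baseline will be summarized by treatment arm", on the ITT and PP sets; the immunogenicity tables use the Safety set.

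**Protocol description.** Protocol 5.2.3.3 speaks of patients who develop ADA and of antibody formation. The analysis list in Protocol 8.5.3.5 counts patients positive at any time.

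**The concern.** Patients must be adalimumab naïve (Protocol 5.3.1, criterion 6), so a positive result before the first dose cannot be a response to either study product. Under the SAP rule, such a subject who tests positive again is indistinguishable from one who seroconverted on treatment. Immunogenicity is sampled at Week 2 (Protocol Table 1). As nothing removes baseline-positives from the risk set, one who is still positive then would become a Kaplan-Meier event at that visit.

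Three things are at stake.

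- The reported ADA level is raised in both arms.
- The arm difference is diluted, which makes the products look more alike. In a biosimilar comparison that is the less cautious direction. Protocol 5.2.1 says that the kinetics of the immune response, including time to ADA, will contribute to the biosimilarity claim.
- The ADA-positive versus ADA-negative splits for efficacy, PK and safety mix pre-existing with induced reactivity. Randomization gives no protection there, because ADA status is not randomized.

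The separate baseline table does not resolve this: two marginal tables cannot show which post-dose positives were already positive.

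**Working it through.** The plan states no figure for ADA, so there is none to reproduce. Its precision figures (12.0% and 9.0%) concern AESI incidence and do not enter here.

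**Inputs**
- n = 130 per arm (Protocol 8.1, SAP 7.1).
- b = share positive at baseline: not in the documents; assumed 0-10%.
- q = share of baseline-positives who stay positive after dosing regardless of treatment: not in the documents; 1 (the extreme) and 0.5 shown.
- t = incidence among baseline-negatives: not in the documents; 30% assumed, other values below.

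**Formulas**
- SAP-defined rate = b[q + (1−q)t] + (1−b)t = t + bq(1−t).
- If b and q are equal in both arms, a true difference among baseline-negatives is multiplied by (1 − bq).
- 95% range for chance imbalance in baseline positivity = 1.96·√(2b(1−b)/n).
- With q = 1, that imbalance enters the reported ADA difference multiplied by (1−t), here 0.7, because a share t of those subjects would have turned positive anyway.

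**Results at t = 30%** (the 10-point difference is 40% versus 30%)

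| b | SAP rate, q=1 | SAP rate, q=0.5 | 10-point difference, q=1 | Chance imbalance in baseline positivity | Carried into ADA difference |
|---|---|---|---|---|---|
| 0% | 30.0% | 30.0% | 10.0 | 0 | 0 |
| 2% | 31.4% | 30.7% | 9.8 | ±3.4 | ±2.4 |
| 5% | 33.5% | 31.8% | 9.5 | ±5.3 | ±3.7 |
| 10% | 37.0% | 33.5% | 9.0 | ±7.3 | ±5.1 |

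Example, b = 10%, q = 1: 0.30 + 0.10 × 0.70 = 0.370. Per arm, 0.10 × 130 = 13 subjects positive before dosing are among 0.370 × 130 = 48.1 ADA-positives, or 27%. The imbalance is 1.96·√(2 × 0.10 × 0.90/130) = 7.3 points, and 7.3 × 0.7 = 5.1.

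**Other incidences (b = 10%, q = 1).** The excess bq(1−t) is 9.0 points at t = 10%, 4.0 at t = 60% and 1.0 at t = 90%.

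**Precision.** The Wald 95% half-width for an arm difference, 1.96·√(2p(1−p)/n), is 11.1 points at p = 30% and 11.7 at p = 37.0% with 130 per arm. Among baseline-negatives only (117 per arm at b = 10%, p = 30%) it is also 11.7.

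**Denominator.** If induced cases are counted over all treated subjects and no baseline-positive is boosted, the rate is (1−b)t = 0.90 × 30% = 27.0%, and a 10-point difference is still 9.0. Only the baseline-negative denominator returns 30.0% and 10.0 points.

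**The case against.** **The SAP follows the protocol's analysis list.** Protocol 8.5.3.5 does count patients positive at any time, and the listed endpoint is ADA to adalimumab, not treatment-emergent ADA. This stands as a reason to keep that count. It does not supply the quantity described in Protocol 5.2.3.3.

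**The effect is small and every rate is assumed.** Dilution of 0.2 to 1.0 point (b = 2% to 10%) is minor against a half-width above 11. At least 80% of patients are biologic naïve under the 20% cap, so baseline positivity near zero cannot be excluded. All of this stands; it limits the size, not the definitional mismatch.

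**Baseline is not ignored.** It is tabulated by arm, counts are given by visit, and all data are listed by subject (SAP 11.3), so a chance imbalance would be visible. True, but no planned table gives a treatment-emergent rate.

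**Stronger readings a reader might infer**
- That the definition favours one product: not supported, because randomization equalizes baseline positivity in expectation.
- That chance imbalance adds 3.4 to 7.3 points of noise to the ADA comparison: those figures describe baseline positivity itself. About 2.4 to 5.1 points carry through, and not on top of the usual interval, whose half-width moves only from 11.1 to 11.7 at b = 10%.
- That the SAP labels these positives a response to treatment: it does not. That reading comes from the protocol's description and from a time-to-event analysis starting on Day 1.

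**Conclusion.** The point holds as a mismatch of definition. Applied as written, the SAP rule counts pre-existing reactivity as on-treatment ADA, while the protocol's rationale describes antibodies that develop. The numbers are illustrations resting on assumed b, q and t. The SAP rate exceeds 30% by at most 7.0 points for b up to 10%, or 3.5 points if half of the baseline-positives stay positive. A 10-point difference loses at most 1.0 point. All of it vanishes as b approaches zero, and the excess is slight if incidence is very high.

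The comparison is descriptive, with no test or margin, so no formal conclusion is overturned. The change is still worth making because immunogenicity is a stated comparative objective, and because the ADA-status splits have no protection from randomization. SAP Section 18 and the appendices are not in the text available; nothing available points to an ADA definition there.

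**What to change.** Amend the SAP before unblinding:

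1. **Treatment-induced ADA:** baseline negative with at least one post-dose positive. Denominator: baseline-negative Safety-set subjects with a post-dose result.
2. **Treatment-boosted ADA,** reported separately: baseline positive with a pre-specified titer rise, justified from the assay. Denominator: baseline-positive subjects.
3. Run time to ADA in baseline-negative subjects.
4. Use treatment-emergent status (induced or boosted) for the splits in SAP 15.3.2.1, 15.3.3.1 and 16.6.
5. Use post-dose titers only for the quartiles in 15.3.2.1. At present a subject positive only before dosing is ADA-negative under 15.3.2 yet can have a non-zero titer there.
6. Show baseline ADA and NAb status on the Safety set, and treat NAb in the same way as ADA.
7. Keep any post-dose positive as a supportive row, to match Protocol 8.5.3.5.

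The cost is SAP wording and derived flags for ADA and NAb. No new sample is needed. If baseline positivity proves to be near zero, the tables will hardly change.
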